5.3 STUDY INTERVENTION COMPLIANCE

The study will be completed by a new resident each year but the PI will have direct oversight of the resident to ensure that the protocol is adhered to. Compliance of the device will be self-reported by the participant.

5.4 CONCOMITANT THERAPY

No concomitant therapy should take place during the study.

6 STUDY INTERVENTION DISCONTINUATION AND SUBJECT DISCONTINUATION/WITHDRAWAL

6.1 DISCONTINUATION OF STUDY INTERVENTION

If the adverse effects are significant, individual participants will be asked to terminate the study. Otherwise, the study may be terminated early due to difficulty in enrollment, per discretion of the PI.

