1 PROTOCOL SUMMARY

1.1 SYNOPSIS

Title:	Spectacle lenses in concussed kids
Study Description:	Many kids who have sustained a concussion still experience symptoms months after the event. This study will examine if certain types of lenses in glasses will help alleviate those symptoms.
Objectives:	Compare symptoms of concussed kids after wearing different types of glasses, one of which is a control.
Endpoints:	3 month follow up phone call
Study Population:	9-17 year olds who have sustained a concussion and are symptomatic
Phase:	3
Description of Study Intervention:	Different types of glasses lenses that are already commercially available and are used routinely in concussion patient.
Study Duration:	2-3 years, largely dependent on ability to recruit subjects
Subject Duration:	3 months

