1.2 SCHEDULE OF ACTIVITIES (SOA)

1. Participants are recruited through routine eye exams at concussion clinic
2. If a patient is eligible for study, an investigator will reach out to the patient at that time to present patient with the opportunity to enroll in the study. The patient has 1 week from that date to decide.
3. Once consents are signed and subject is officially enrolled, they will be randomized into 1 of 3 possible lens options.
4. Investigators will then order the lenses from the supplier to then be fit in patient's glasses
5. Dispense of glasses to participant (timing will vary due to dependence on supplier). Repeat concussion survey at dispense.

6. Masked in-person exam 4-6 weeks from dispense of glasses
 - a. Standard binocular vision assessment for primary and secondary measurements
7. Last assessment: 3 month phone call after dispense of glasses for last concussion survey

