4 STUDY POPULATION

4.1 INCLUSION CRITERIA

- 9-17 years of age
- Sustained a concussion ≥ 6 weeks ≤ 16 weeks from date of ophthalmic exam
 - Criteria for concussion: clinically diagnosed by physician
- Best corrected visual acuity: 20/30 in both eyes at near; 20/25 in each eye at distance
- Minimum Stereopsis: 500" global
- CISS score ≥ 16
- Refractive error at least $\pm 0.50D$ sphere or cylinder
- Ability to clear ≥ 0.50 cycles per minute in monocular accommodative flipper of and binocular accommodative flipper

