6.2 SUBJECT DISCONTINUATION/WITHDRAWAL FROM THE STUDY

Subjects are free to withdraw from participation in the study at any time upon request.

An investigator may discontinue or withdraw a subject from the study for the following reasons:

- Significant study intervention non-compliance
- If any clinical adverse event (AE), laboratory abnormality, or other medical condition or situation occurs such that continued participation in the study would not be in the best interest of the subject

Subjects who sign the informed consent form and are randomized but do not receive the study intervention may be replaced. Subjects who sign the informed consent form, and are randomized and receive the study intervention, and subsequently withdraw, or are withdrawn or discontinued from the study, will not be replaced.

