8 STATISTICAL CONSIDERATIONS

8.1 STATISTICAL HYPOTHESES

- Primary Efficacy Endpoint(s):

The CISS score will be the efficacy endpoint. A CISS score of zero is considered complete resolution of the problem.

- Secondary Efficacy Endpoint(s):

TBD

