8.3.4 SAFETY ANALYSES

If the patient scores well below baseline, 10 points or more at the follow up appointment, then we may remove the patient from the study.

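### Sections 6.1, 6.2 and 8.3.4 take participants out of the study, not only off the lenses, and no section keeps the 3-month survey call for them

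*Protocol*

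**What the plan says.** Three places in the protocol deal with participants who should not, or do not, carry on with the lenses.

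- **Section 6.1** is headed as discontinuation of the study intervention, but its rule concerns the study: "If the adverse effects are significant, individual participants will be asked to terminate the study". This one is directive.
- **Section 6.2** is permissive: "An investigator may discontinue or withdraw a subject from the study for the following reasons". The reasons include "Significant study intervention non-compliance" and adverse events or other medical conditions. Anyone withdrawn after receiving the lenses is not replaced.
- **Section 8.3.4**, under safety analyses, is also permissive: "If the patient scores well below baseline, 10 points or more at the follow up appointment, then we may remove the patient" from the study.

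The synopsis (1.1) gives the endpoint as "3 month follow up phone call". The schedule (1.2) makes that call the last assessment. Before it comes a "Masked in-person exam 4-6 weeks from dispense of glasses", which step 6a says serves primary and secondary measurements. Sections 2.1 and 8.1 name the CISS as the main outcome, and 8.1 fixes its direction: "A CISS score of zero is considered complete resolution of the problem". Entry requires "CISS score ≥ 16" (4.1), and step 5 of the schedule repeats the survey when the glasses are dispensed.

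**The concern.** Stopping a treatment and leaving a trial are different events. A randomised comparison needs outcomes from everyone randomised, including those who could not tolerate the lenses or did not wear them. If such participants leave the study, their 3-month value is missing for a reason that may depend on the lens received, and the groups compared are no longer the groups randomised.

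This belongs in the protocol. A statistical analysis plan can say how missing values are handled, but it cannot recover calls that were never made.

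Section 8.3.4 needs separate attention because its trigger is a score. If that score is the CISS, removal depends on the primary outcome itself, whichever direction was intended.

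**Working it through.** The protocol gives no figure to reproduce: section 8.2 bases the sample size on funding. The check is mainly a reading of the text, with some simple arithmetic.

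**1. Does any section keep the call?**

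- Section 2.3.1 mentions stopping study treatment so that other interventions can be pursued. It says nothing about later assessments.
- Section 6.3 sets out contact attempts, but for missed visits, not for participants whom the study has removed.
- Section 7.2.4 continues after exit, but only for adverse events. New events are recorded for 7 days (non-serious) or 30 days (serious) after participation ends.

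None of these keeps the 3-month survey.

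**2. Timing.** Three months = 365.25 / 7 / 4 = 13.0 weeks after dispensing. For a removal at the 4-6 week exam:

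- at week 6: 13.0 − 6 = 7.0 weeks of follow-up lost, 7.0 / 13.0 = 54%
- at week 4: 13.0 − 4 = 9.0 weeks lost, 9.0 / 13.0 = 69%

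After exit at week 6, adverse event recording ends at 6 + 1 = 7 weeks or 6 + 30/7 = 10.3 weeks. Even the later date is about 2.8 weeks before the call, so that contact would not capture the 3-month value by chance.

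**3. Cost per removal.** Total enrolment is 90 (3.2) over 3 lens options (1.2). The allocation ratio is not stated. If it is equal, 90 / 3 = 30 per arm, and one removal is 1 / 30 = 3.3% of an arm's 3-month data.

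**4. What 8.3.4 does under each reading.**

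| Reading of 8.3.4 | Consequence |
|---|---|
| CISS, literal direction, baseline = entry score | Full resolution at 4-6 weeks is a fall of at least 16 − 0 = 16, which is at least 10, so the rule is met |
| CISS, literal direction, baseline = dispense score | No floor of 16 applies. A child at 8 on dispensing who reaches 0 has fallen 8 and does not meet the rule |
| CISS, worsening intended | Those 10 or more points higher may be removed, so removal still depends on the outcome |
| Another instrument | Direction and meaning cannot be determined from the protocol |

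**5. Direction only, on assumed inputs.** Suppose the CISS change is normal with SD 10 at both times, with the same mean at both, −4 in control and −10 in active (true difference −6.0). Let the correlation between 4-6 weeks and 3 months be r = 0.5 to 0.9, apply the removal rule every time, and compare only those who remain.

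- Literal rule (fall of 10 or more): removed are Φ(−0.6) = 27% of control and Φ(0) = 50% of active. The mean of those remaining shifts by 10r·φ(a)/(1 − Φ(a)) with a = (−10 − mean)/10: 4.59r in control and 7.98r in active. The difference becomes −6 + 3.39r, from about −4.3 to −2.9.
- Worsening rule (rise of 10 or more): removed are 8% and 2%. The shifts are −1.63r and −0.55r. The difference becomes −6 + 1.08r, from about −5.5 to −5.0.
- With equal means in both arms (−8 and −8), neither rule creates a difference.

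None of these means, the SD or the correlations is in the protocol. The illustration shows that the pull is towards no difference under these assumptions. It does not estimate bias in this trial.

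**The case against.** The case on the other side has real content.

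- **The rules may seldom operate.** Sections 6.2 and 8.3.4 say only that removal may happen. Section 6.1 is directive, but section 2.3.1 anticipates no adverse events. This stands, and it limits the likely number lost.
- **Section 6.1 may be loosely worded.** Its heading concerns the intervention, and section 2.3.1 treats stopping treatment as a step of its own. The authors may have meant only that the lenses stop. That is possible, but the sentence as written sends the participant out of the study, and sites will follow the sentence.
- **The endpoint may not be lost entirely.** Step 6a assigns primary measurements to the 4-6 week exam, and section 8.1 gives the CISS no time point. A participant removed at that visit may already have supplied an earlier value, which could partly support a missing-at-random analysis. This stands. It does not replace the 3-month value that the synopsis names.
- **The survey at the call is not called the CISS.** The schedule speaks of a concussion survey. Reading it as the CISS rests on sections 2.1 and 8.1.

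A reader might infer that the protocol sets out to remove children who improve, and that everyone fully resolved at 4-6 weeks goes. The text does not support either as a firm statement. Section 8.3.4 names no instrument, its place under safety suggests that worsening was meant, and the second inference also needs the entry score to be the baseline, although the survey is repeated at dispensing.

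**Conclusion.** The point holds as a defect in the follow-up rules. One section directs and two permit exit from the study for tolerability, adherence or a score, and nothing in the protocol keeps the 3-month call, or the 4-6 week exam for those who stop before it. Section 8.3.4 is badly fixed on its own account: instrument, baseline and direction are all open. If the score is the CISS, both directions make removal depend on the outcome.

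The size that can be stated is limited: 7 to 9 weeks of follow-up lost for a removal at the 4-6 week visit, and 3.3% of an arm's 3-month data per removal under equal allocation. How many would be removed, and how far the comparison would be biased, cannot be derived from the protocol. It would go too far to conclude that the result will be materially biased or that the primary outcome is wholly lost. The change should be made because the lost data cannot be recovered later and keeping them is cheap.

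**What to change.** - In 6.1, 6.2 and 8.3.4, separate stopping lens wear from leaving the study.
- State that every participant who stops the lenses, is non-compliant or meets the 10-point rule still receives the 3-month CISS call and, where feasible, the masked 4-6 week exam, unless they refuse contact.
- Reword 8.3.4 so that a CISS score at the 4-6 week visit that is 10 points or more higher (worse) than a named baseline, either the entry or the dispense score, triggers a clinical review of lens wear and not removal from the study.

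The investigator's freedom to stop the lenses and the participant's right to withdraw are unchanged. The cost is protocol wording in three sections, one short phone call per affected participant and, where feasible, a visit that is already scheduled.

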6.2 SUBJECT DISCONTINUATION/WITHDRAWAL FROM THE STUDY

Subjects are free to withdraw from participation in the study at any time upon request.

An investigator may discontinue or withdraw a subject from the study for the following reasons:

- Significant study intervention non-compliance
- If any clinical adverse event (AE), laboratory abnormality, or other medical condition or situation occurs such that continued participation in the study would not be in the best interest of the subject

Subjects who sign the informed consent form and are randomized but do not receive the study intervention may be replaced. Subjects who sign the informed consent form, and are randomized and receive the study intervention, and subsequently withdraw, or are withdrawn or discontinued from the study, will not be replaced.

6.3 LOST TO FOLLOW-UP

A subject will be considered lost to follow-up if he or she fails to return for 2 scheduled visits and is unable to be contacted by the study site staff.

The following actions must be taken if a subject fails to be available for a required study visit:

- The site will attempt to contact the subject and reschedule the missed visit and counsel the subject on the importance of maintaining the assigned visit schedule and ascertain if the subject wishes to and/or should continue in the study.
- Before a subject is deemed lost to follow-up, the investigator or designee will make every effort to regain contact with the subject (where possible, 3 telephone calls and, if necessary, a certified letter to the subject's last known mailing address or local equivalent methods). These contact attempts should be documented in the subject's medical record or study file.
- Should the subject continue to be unreachable, he or she will be considered to have withdrawn from the study with a primary reason of lost to follow-up.

7 STUDY ASSESSMENTS AND PROCEDURES

7.1 STUDY ASSESSMENTS

Study assessments will be done periodically.

7.2 ADVERSE EVENTS AND SERIOUS ADVERSE EVENTS

7.2.1 DEFINITION OF ADVERSE EVENTS (AE)

Adverse event means any untoward medical occurrence associated with the use of an intervention in humans, whether or not considered intervention-related (21 CFR 312.32 (a)).

7.2.2 DEFINITION OF SERIOUS ADVERSE EVENTS (SAE)

An adverse event (AE) is considered “serious” if, in the view of either the investigator or sponsor, it results in any of the following outcomes:

- Death
- A life-threatening adverse event (of note, the term “life-threatening” refers to an event in which the subject was at risk of death at the time of the event, rather than to an event which hypothetically might have caused death if it were more severe)
- inpatient hospitalization or prolongation of existing hospitalization
- a persistent or significant incapacity or substantial disruption of the ability to conduct normal life functions
- or a congenital anomaly/birth defect.

Important medical events that may not result in death, be life-threatening, or require hospitalization may be considered serious when, based upon appropriate medical judgment, they may jeopardize the subject and may require medical or surgical intervention to prevent one of the outcomes listed in this definition. Examples of such medical events include allergic bronchospasm requiring intensive treatment in an emergency room or at home, blood dyscrasias or convulsions that do not result in inpatient hospitalization, or the development of drug dependency or drug abuse.

7.2.3 CLASSIFICATION OF AN ADVERSE EVENT

7.2.3.1 SEVERITY OF EVENT

For adverse events (AEs), the following guidelines will be used to describe severity:

- **Mild** – Events require minimal or no treatment and do not interfere with the subject’s daily activities.
- **Moderate** – Events result in a low level of inconvenience or concern with the therapeutic measures. Moderate events may cause some interference with functioning.
- **Severe** – Events interrupt a subject’s usual daily activity and may require systemic drug therapy or other treatment. Severe events are usually potentially life-threatening or incapacitating. Of note, the term “severe” does not necessarily equate to “serious.”

7.2.3.2 RELATIONSHIP TO STUDY INTERVENTION

All adverse events (AEs) must have their relationship to study intervention assessed by the clinician who examines and evaluates the subject based on temporal relationship and his/her clinical judgment. The degree of certainty about causality will be graded using the categories below. In a clinical trial, the study product must always be suspect.

- **Related** – The AE is known to occur with the study intervention, there is a reasonable possibility that the study intervention caused the AE, or there is a temporal relationship between the study

intervention and event. Reasonable possibility means that there is evidence to suggest a causal relationship between the study intervention and the AE.

- **Not Related** – There is not a reasonable possibility that the administration of the study intervention caused the event, there is no temporal relationship between the study intervention and event onset, or an alternate etiology has been established.

7.2.3.3 EXPECTEDNESS

The Principal Investigator will be responsible for determining whether an adverse event (AE) is expected or unexpected. An AE will be considered unexpected if the nature, severity, or frequency of the event is not consistent with the risk information previously described for the study intervention.

7.2.4 TIME PERIOD AND FREQUENCY FOR EVENT ASSESSMENT AND FOLLOW-UP

The occurrence of an adverse event (AE) or serious adverse event (SAE) may come to the attention of study personnel during study visits and interviews of a study subject presenting for medical care, or upon review by a study monitor.

All AEs including local and systemic reactions not meeting the criteria for SAEs will be captured on the appropriate case report form (CRF). Information to be collected includes event description, time of onset, clinician's assessment of severity, relationship to study product (assessed only by those with the training and authority to make a diagnosis), and time of resolution/stabilization of the event. All AEs occurring while on study must be documented appropriately regardless of relationship. All AEs will be followed to adequate resolution.

Any medical condition that is present at the time that the subject is screened will be considered as baseline and not reported as an AE. However, if the study subject's condition deteriorates at any time during the study, it will be recorded as an AE.

Changes in the severity of an AE will be documented to allow an assessment of the duration of the event at each level of severity to be performed. AEs characterized as intermittent require documentation of onset and duration of each episode.

The Study Coordinator will record all reportable events with start dates occurring any time after informed consent is obtained until 7 (for non-serious AEs) or 30 days (for SAEs) after the last day of study participation. At each study visit, the Study Coordinator will inquire about the occurrence of AE/SAEs since the last visit. Events will be followed for outcome information until resolution or stabilization.

7.2.5 ADVERSE AND SERIOUS ADVERSE EVENT REPORTING

All serious adverse events must be reported to the IRB according to regulatory requirements. The Principal Investigator will immediately report to the sponsor any serious adverse event, whether or not considered study intervention related, including those listed in the protocol or package insert and must include an assessment of whether there is a reasonable possibility that the study intervention caused the event. Study endpoints that are serious adverse events (e.g., all-cause mortality) must be reported in accordance with the protocol unless there is evidence suggesting a causal relationship between the study intervention and the event (e.g., death from anaphylaxis). In that case, the investigator must immediately report the event to the sponsor.

All serious adverse events (SAEs) will be followed until satisfactory resolution or until the Principal Investigator deems the event to be chronic or the subject is stable. Other supporting documentation of the event may be requested and should be provided as soon as possible.

7.3 UNANTICIPATED PROBLEMS

7.3.1 DEFINITION OF UNANTICIPATED PROBLEMS (UP)

The Office for Human Research Protections (OHRP) considers unanticipated problems involving risks to subjects or others to include, in general, any incident, experience, or outcome that meets **all** of the following criteria:

- Unexpected in terms of nature, severity, or frequency given (a) the research procedures that are described in the protocol-related documents, such as the Institutional Review Board (IRB)-approved research protocol and informed consent document; and (b) the characteristics of the subject population being studied;
- Related or possibly related to participation in the research (“possibly related” means there is a reasonable possibility that the incident, experience, or outcome may have been caused by the procedures involved in the research); and
- Suggests that the research places subjects or others at a greater risk of harm (including physical, psychological, economic, or social harm) than was previously known or recognized.

7.3.2 UNANTICIPATED PROBLEM REPORTING

The investigator will report unanticipated problems (UPs) to the reviewing Institutional Review Board (IRB). The UP report will include the following information:

- Protocol identifying information: protocol title and number, PI’s name, and the IRB project number;
- A detailed description of the event, incident, experience, or outcome;
- An explanation of the basis for determining that the event, incident, experience, or outcome represents an UP;
- A description of any changes to the protocol or other corrective actions that have been taken or are proposed in response to the UP.

To satisfy the requirement for prompt reporting, UPs will be reported using the following timeline:

- UPs that are serious adverse events (SAEs) will be reported to the IRB within 10 working days of the investigator becoming aware of the event.
- Any other UP will be reported to the IRB within 10 working days of the investigator becoming aware of the problem.

8 STATISTICAL CONSIDERATIONS

8.1 STATISTICAL HYPOTHESES

- Primary Efficacy Endpoint(s):

The CISS score will be the efficacy endpoint. A CISS score of zero is considered complete resolution of the problem.

- Secondary Efficacy Endpoint(s):

TBD

8.2 SAMPLE SIZE DETERMINATION

This was based on the funding we received from the lenses company.

8.3 STATISTICAL ANALYSES

8.3.1 GENERAL APPROACH

TBD

8.3.2 ANALYSIS OF THE PRIMARY EFFICACY ENDPOINT(S)

TBD

8.3.3 ANALYSIS OF THE SECONDARY ENDPOINT(S)

TBD

8.3.4 SAFETY ANALYSES

If the patient scores well below baseline, 10 points or more at the follow up appointment, then we may remove the patient from the study.

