2 INTRODUCTION

2.1 STUDY RATIONALE

The main goal for this study is to determine the effectiveness of anti-fatigue (low additional prescription at near) in treating post-concussion patients for their visual symptoms. The main outcome measurement will be the convergence insufficiency symptom survey (CISS) pre-intervention and post-intervention of the anti-fatigue lenses. This will be compared to the CISS results of single vision glasses (rule out placebo effects)

Other secondary outcome measurement will be objective measurements of vergence ranges and accommodation magnitude and flexibility, reduction of symptoms with single vision glasses alone for low refractive error individuals and the effects of anti-reflective coating.

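### Taken on the CISS, the safety removal rule in section 8.3.4 is met by a 10-point improvement and never by worsening

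*Protocol*

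**What the plan says.** Section 8.3.4 (Safety Analyses) consists of one rule: "If the patient scores well below baseline, 10 points or more at the follow up appointment, then we may remove the patient from the study". Sections 8.3.1, 8.3.2, 8.3.3 and 8.3.5 are marked as still to be determined; this one is not. It is a fixed rule to be applied while participants are on study.

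The rule names no score. The CISS is the natural candidate. Section 2.1 states: "The main outcome measurement will be the convergence insufficiency symptom survey (CISS) pre-intervention and post-intervention of the anti-fatigue lenses". Section 8.1 makes it the efficacy endpoint, and no other measure in the protocol is given a score in points.

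Two places fix its direction. Section 8.1: "A CISS score of zero is considered complete resolution of the problem". Section 4.1 lists "CISS score ≥ 16" among the inclusion criteria.

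Section 6.2 gives two grounds on which an investigator may withdraw a participant: significant non-compliance, and an adverse event or other medical situation "such that continued participation in the study would not be in the best interest of the subject". Participants who have received the intervention and then withdraw, "or are withdrawn or discontinued from the study, will not be replaced".

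The schedule in section 1.2 has a survey at dispense ("Repeat concussion survey at dispense"), a masked in-person exam 4-6 weeks later ("Standard binocular vision assessment for primary and secondary measurements"), and a last survey by telephone at 3 months.

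**The concern.** A safety rule should respond to harm. On a scale where a high score means more symptoms, a rule that responds to scores below baseline responds to benefit. The only removal criterion in the protocol with a numerical threshold therefore points away from the event it is presumably there to catch.

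Two things are at stake. The first is consistent conduct. Section 3.1 names five sites and section 5.3 says a new resident carries out the study each year. Staff who follow the text would consider removing children who have done well; staff who follow the presumed intention would do the opposite. The second is the endpoint. The rule acts on the outcome variable itself, so if it were applied literally before the last survey, whether the 3-month value is observed could depend on how well the child responded.

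**Working it through.** The protocol gives no figure to reproduce here. The check is one of direction.

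**Inputs**
- Threshold: 10 points below baseline (section 8.3.4).
- Best score: 0 (section 8.1).
- Minimum CISS at entry: 16 (section 4.1).
- Assumption: the score in section 8.3.4 is the CISS.

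**The rule as written.** With B the baseline score and F the follow-up score, the condition is B − F ≥ 10, that is, F ≤ B − 10.

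| Case | B | F | B − F | Rule met? |
|---|---|---|---|---|
| Complete resolution from the entry minimum | 16 | 0 | 16 | Yes |
| Smallest qualifying fall from the entry minimum | 16 | 6 | 10 | Yes |
| No change | 16 | 16 | 0 | No |
| Ten points worse | 16 | 26 | −10 | No |

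**In general**
- Worsening means F > B, so B − F < 0, which is never 10 or more. This holds for any baseline value.
- Complete resolution means F = 0, so B − F = B. With an entry baseline, B ≥ 16 ≥ 10, so every complete resolution meets the rule. This statement needs the entry score as baseline: a baseline of 9 or less could not fall by 10.
- For entry scores of 16 to 25, the bound B − 10 runs from 6 to 15. Meeting the rule then means scoring below the trial's own entry threshold of 16.

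**The rule reversed.** With F − B ≥ 10, a child who enters at 16 meets it at 26 or more. Complete resolution gives F − B = −B, which is −16 or lower, and never meets it. Every case that meets it is a worsening.

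**Fit with section 6.2.** A 10-point improvement is not non-compliance, and it is not an event that makes continuing contrary to the child's interest. Only worsening could fit the second ground. The literal rule therefore also sits badly with the protocol's own list of withdrawal grounds.

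**When endpoint data could be lost.** If the rule is applied at the 4-6 week exam, a removal precedes the 3-month survey. If it is applied at the 3-month call, that is already the last assessment and nothing later is lost. The first case further assumes that the concussion survey in section 1.2 is the CISS, which the protocol never says, and that the CISS is taken at the 4-6 week exam, where section 1.2 does not name it.

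**The case against.** The strongest reply is that the meaning is plain in context. The sentence stands under a safety heading, and scoring below baseline is a common loose way of saying that someone has done worse. Removal is optional, and a clinician applying a safety rule is unlikely to remove a child whose symptoms have gone. Much of this stands. Worsening was very probably meant, and that lowers the severity. It does not make the rule correct as written: it carries a numerical threshold, and several sites with changing staff are to apply it.

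The score is also inferred. If another instrument was meant, its direction is unknown and the argument about direction does not apply. But the protocol then gives no instrument with which to apply the rule, so naming the score is needed either way.

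A reader might infer that children who get worse are unprotected. The protocol does not support that. Section 2.3.1 allows study treatment to be stopped in favour of other care, section 6.1 covers significant adverse effects, section 6.2 covers withdrawal in the child's interest, and section 7.2.4 records deterioration as an adverse event. None of these uses a score threshold, but together they cover worsening.

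A reader might also infer that the rule will bias the treatment comparison by discarding responders. That needs staff to apply the literal reading against its evident purpose, the CISS to be taken at the 4-6 week exam, the discretion to be used, and the removed child not to be called at 3 months. Section 6.2 says that withdrawn participants are not replaced; it does not say that data collection from them stops. The loss is possible, but nothing in the protocol shows how often it would occur.

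Finally, the rule does not say which pre-treatment value is the baseline or which contact is the follow-up appointment. Such detail is commonly left to a statistical analysis plan, which is not at hand here, so it is not a separate fault.

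**Conclusion.** The point holds as an error of direction in a fixed operational rule. On the CISS, section 8.3.4 is met by a fall of 10 or more points, including every complete resolution from an entry baseline, and by no worsening of any size. This rests on one inference, that the score is the CISS; the direction of the CISS comes from the protocol itself.

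Severity is minor to moderate. The number of participants who would be removed cannot be derived from the protocol, and no size of bias is claimed. The possible loss of responders before the 3-month survey is conditional on literal use at the 4-6 week exam and on the concussion survey being the CISS.

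**What to change.** Reword section 8.3.4 so that it names the CISS and triggers on an increase of 10 or more points above baseline, with the investigators confirming that 10 is the threshold they want. Add that a participant who meets the rule may stop wearing the lenses but is still called for the 3-month survey. The same sentence can usefully say which value is the baseline and at which visit the rule applies.

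The cost is one or two sentences in a protocol amendment, with the IRB approval that any amendment needs. No new visit is required, because the 3-month call is already scheduled.
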